8.6.2 Questionnaire interviewed by investigator or designee

The Skindex-10 Scale and 5-D Itch scale are both multidimensional scales not only access pruritus intensity but measure the impact of pruritus on patients. The Skindex-10 evaluate how the patient's itch affects three important domains of quality of life including 3 domains (disease, mood/emotional distress, and social functioning) as noted in [Appendix B](#). Subjects filled one of seven bubbles ("0 [never bothered], 1, 2, 3, 4, 5, and 6 [always bothered]") for each of the questions. The total score was the sum of the numeric value of each answered question ranging from 0 to 60, with higher scores indicating worse itch-related quality of life. The 5-D itch scale include 5 domains (the duration, degree, direction, disability, and distribution) as noted in [Appendix C](#), with a total score ranging from 5 (no itching) to 25 (maximum severity).

The Skindex-10 and 5-D Itch scale will be performed when patients were in the dialysis unit. The investigator or designee will conduct a face-to-face interview to assist the subject complete the Skindex-10 Scale and 5-D Itch scale. Before the interview, the investigator or designee will be trained by the medical monitor to ensure the accuracy and maintain the consistency of the interview across individuals. Subjects will complete the questionnaire without input on the answers from the study team.

The questionnaire interview will be conducted every 2 weeks at day 1 (Visit 1), day 15 (Visit 5), and day 29 (Visit 7) in Part A, and day 1 (Visit 1), day 15 (Visit 3), day 29 (Visit 5), day 43 (Visit 7), day 57 (Visit 9) in Part B as noted in the schedule of assessments ([Table 2.1](#), [Table 2.2](#)).

In practice, the order of the procedures is recommended as follows but may be adjusted upon investigator's judgement: (1) Before dialysis: vital signs, blood sampling for the PK and

laboratory tests (2) During dialysis: Skindex-10 Scale and 5-D Itch scale (3) After dialysis: body weight, physical examination, and other safety assessment procedures.

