APPENDIX B Skindex-10 Scale

During the past WEEK, how often have you been bothered by:

1. Your itching
2. The persistence/recurrence of your itching
3. The appearance of your skin from scratching
4. Frustration about your itching
5. Being annoyed about your itching
6. Feeling depressed about your itching
7. Feeling embarrassed about your itching
8. The effects of your itching on your interactions with others (for example: interactions with family, friends, close relationships, etc.)
9. The effects of your itching on your desire to be with people
10. The effect of your itching making it hard to work or do what you enjoy

Patients fill one of seven bubbles (“0 [never bothered], 1, 2, 3, 4, 5, and 6 [always bothered]”) for each of the questions. The total score is the sum of the numeric value of each answered question. The domain scores are sums of the following: disease domain (questions 1 to 3), mood/emotional distress domain (question 4 to 6), and social functioning domain (questions 7 to 10)

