Objectives	
Primary Objective – Part A
 
To investigate the safety, local tolerability, and PK of 4-week, multiple dermal applications of LT5001 drug product to hemodialysis patients with UP.
 
 • Part A Primary Endpoint - Nature and severity of AEs and number of patients with AEs. • Part A Secondary Endpoints - [REDACTED] - [REDACTED] - Change in mean Worst Itching Intensity from baseline to the end of Week 4 using NRS. - Reduction of itch intensity as assessed by the proportion of patients reduced NRS from baseline (≥ 2 points, ≥ 3 points, or ≥ 4 points) with respect to the weekly mean of the daily 24-hour Worst Itching Intensity NRS score from baseline to the end of Week 4. - Improvement in itch-related quality of life as assessed by the change from baseline in 5-D Itch Scale score to the end of Week 4. - Improvement in itch-related quality of life as assessed by the change from baseline in the total Skindex-10 Scale score to the end of Week 4. 
Primary Objective – Part B
 
To investigate the safety and efficacy of 8-week, multiple dermal applications of LT5001 drug product to hemodialysis patients with UP.
 
 • Part B Primary Endpoint - Change from baseline to end of Week 8 in mean Worst Itching Intensity using NRS. • Part B Secondary Endpoints - Reduction of itch intensity as assessed by the proportion of patients reduced NRS from baseline with respect to the weekly mean of the daily 24-hour Worst Itching Intensity NRS score from baseline to end of Week 8. - Improvement in itch-related quality of life as assessed by the change from baseline in 5-D Itch Scale score to the end of Week 8. - Improvement in itch-related quality of life as assessed by the change from baseline in total Skindex-10 Scale score to the end of Week 8. - Nature and severity of AEs and number of patients with AEs.
------------	--

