10.2 Secondary efficacy analyses

In Part A, the secondary efficacy endpoints will be summarized using descriptive statistics. Statistical comparisons will only be performed in park B using a two-sided test at a significance level of 5%, and 95% CI and a P-value will be reported in case of efficacy analysis.

5-D Itch Scale

The 5-D itch scale was developed as a brief but multidimensional questionnaire designed to be useful as an outcome measure in clinical trials. The five dimensions are degree, duration, direction,

QMS Document Name: Statistical Analysis Plan	Page 18 of 33
QMS No (include version ref): STF-015-GL.02	Document date: 09JUL2019
CONFIDENTIAL	

disability and distribution. The duration, degree and direction domains each included one item, while the disability domain had four items. All items of the first four domains were measured on a five-point Likert scale.

The five-point Likert scale are rated from 1 to 5 points. For disability domain, the highest score on any of the four items will be used. For the distribution domain, the number of affected body parts is tallied (potential sum 0–16) and the sum is sorted into five scoring bins: sum of 0–2 = score of 1, sum of 3–5 = score of 2, sum of 6–10 = score of 3, sum of 11–13 = score of 4, and sum of 14–16 = score of 5. The total score of 5-D itch will be the sum of the 5 domains, ranging from 5 to 25 points.

5-D itch scale will be assessed at Visit 1, Visit 5, Visit 7 in Part A and Visit 1, Visit 3, Visit 5, Visit 7, Visit 9 (End of study) in Part B. Baseline of 5D itch score will be assessed at Visit 1.

Change from baseline in 5-D Itch Scale score at week 4 in Part A and Week 8 in Part B (total score and score for each domain) will be summarized by treatment group and visit.

In Part A and B, mixed-effect model repeated measure analysis of covariance will be performed to compare the treatment group considering covariates (baseline itch and prior anti-itch medication use).

Skindex-10 scale

Skindex-10 consists of 10 questions used to evaluate how the patient's itch affects three important domains of quality of life.

The total score of skindex-10 scale is the sum of the numeric value of each answered question. The domain scores are sums of the following: disease domain (questions 1 to 3), mood/emotional distress domain (question 4 to 6), and social functioning domain (questions 7 to 10)

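### The Skindex-10 total counts each unanswered item as 0, so a partly completed form gives a total that is too low rather than missing

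*SAP*

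**What the plan says.** SAP 10.2 states that "Skindex-10 consists of 10 questions" and scores them in one sentence: "The total score of skindex-10 scale is the sum of the numeric value of each answered question". Protocol Appendix B has the same rule: "The total score is the sum of the numeric value of each answered question". Protocol 8.6.2 repeats it with a range, "The total score was the sum of the numeric value of each answered question ranging from 0 to 60", and gives the direction of the scale, "with higher scores indicating worse itch-related quality of life". Each item is marked on a seven-point response, "0 [never bothered], 1, 2, 3, 4, 5, and 6 [always bothered", and Appendix B shows no box for an item that does not apply.

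The domain scores are described as sums of listed items: "disease domain (questions 1 to 3), mood/emotional distress domain (question 4 to 6), and social functioning domain (questions 7 to 10". That sentence does not contain the word answered and does not say what happens to a blank.

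The total feeds a named secondary endpoint in both parts. For Part B it is the "change from baseline in total Skindex-10 Scale score to the end of Week 8". SAP 10.2 compares the arms in Part B with a repeated-measures mixed model and a two-sided 5% test.

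SAP 5.2 and protocol 10.9 carry the last observation forward, as a general rule, for missing efficacy data. Neither gives an item-level rule for Skindex-10, and neither document sets a minimum number of answered items. The itch NRS, by contrast, has both elements in SAP 10.1: the weekly sum is divided by the number of days with a score, and the week is set to missing if more than 3 days are absent.

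**The concern.** A sum over answered items gives a blank the value 0, which on this scale means no bother at all. Followed literally, the rule treats silence as the best possible answer. Because the form still produces a number, nothing downstream marks it as incomplete: the total is not missing, so carry-forward is not triggered, and the mixed model takes the low value as observed.

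The direction of the error depends on the visit. A blank after baseline lowers the later total and looks like improvement. A blank at Visit 1 lowers the baseline and makes the later change look like worsening. At stake is the accuracy of a tested secondary endpoint in Part B and of the same endpoint in Part A. The primary endpoint of neither part is touched. A questionnaire missed altogether is a different case: no question was answered, so the general missing-data rule applies.

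**Working it through.** **Inputs from the documents.** Ten items, each 0 to 6; total equals the sum of answered items; higher is worse; range 0 to 60. **Assumed, because the documents give no figures:** true item scores of 2 to 4, mean totals of 20 to 40, and item-blank rates of 5% and 10%.

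**1. The plan's own range.** 10 × 0 = 0 and 10 × 6 = 60, so the stated range reproduces, but only for a fully answered form. With k blanks the highest attainable total is 60 − 6k: 54, 48 and 42 for k = 1, 2 and 3.

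**2. One patient with no true change.** If every item has true score s and k items are blank after baseline, the recorded total is (10 − k)s and the recorded change is (10 − k)s − 10s = −ks.

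| s | True total | k = 1 | k = 2 |
|---|---|---|---|
| 2 | 20 | −2 | −4 |
| 3 | 30 | −3 | −6 |
| 4 | 40 | −4 | −8 |

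The same blanks at Visit 1 only give +ks; for example, s = 4 and k = 2 give +8. An item blank at both visits with an unchanged true score gives no false change, because it drops out of both totals.

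**3. Between arms.** If a share p of items is blank after baseline, unrelated to the item score, the expected recorded mean is (1 − p)T for a true mean total T, so the error in that arm is −pT.

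- Equal blank rates, no true effect: the errors cancel and there is no false difference.
- Equal rates of 10%, true means of 24 on LT5001 and 30 on placebo (difference −6): 0.9 × 24 − 0.9 × 30 = 21.6 − 27.0 = −5.4. A real difference shrinks.
- 10% on LT5001 and 5% on placebo, no true effect: the false difference is −(0.10 − 0.05)T, which is −1.0, −1.5 and −2.0 for T = 20, 30 and 40. With the rates reversed it is +1.0, +1.5 and +2.0.

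**4. Under a prorated rule.** Total = (sum of answered items) × 10 / (number answered). For s = 3 and one blank: 27 / 9 × 10 = 30. For s = 4 and two blanks: 32 / 8 × 10 = 40. The false change is 0 in both cases.

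**The case against.** The strongest reply is that the scoring sentence describes the instrument and not a missing-data rule. Protocol 8.6.2 pairs it with a 0 to 60 range that is attainable only on a complete form, and no section says in words that a blank is scored 0. This softens the tone but leaves the result: a programmer who follows the sentence gets the low total, and no other text tells them to do anything else. SAP 5.2 does not say whether carry-forward works on items or totals, but a total that has been computed is not missing.

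The second reply is that blanks should be few. Protocol 8.6.2 has trained staff assist completion face to face, and inclusion criterion 10 requires patients to be able to complete questionnaires. The bar on study-team input concerns the content of answers and does not stop staff pointing out a blank. This stands, and it limits the size. It does not remove the point, since nothing requires every item to be answered. The 5-D scale in Appendix C does offer a not-applicable box for leisure, housework and work, while Skindex-10 asks about similar activities without one. Whether patients leave those items blank is not known from the documents.

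A reader might also infer three stronger things that the documents do not support:

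- *The rule favours LT5001.* The sign depends on the visit at which the blank occurs and on which arm has more blanks. In a randomised, double-blind comparison there is no stated reason to expect an imbalance in either direction.
- *The domain scores follow the same rule by text.* The domain sentence is silent; a blank could equally make a domain missing.
- *The per-patient shifts of 2 to 8 points are errors in the treatment effect.* They are errors in single records and are diluted by every complete form.

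**Conclusion.** The point holds. The stated rule gives a wrong value for a partly completed Skindex-10, and nothing else in the plan corrects it. The individual error equals the true score of the skipped items. The effect on the comparison is probably small: attenuation of −6 to −5.4 at 10% blanks in both arms, or a false difference of about 1 to 2 points out of 60 with 10% against 5%. These sizes rest on assumed blank rates and mean totals, on blanks occurring only after baseline, and on blanks being unrelated to item score. Rates below those assumed would give smaller effects. It is a scoring defect in a secondary endpoint, worth correcting before unblinding because a rule chosen afterwards would be open to challenge.

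**What to change.** Before unblinding, replace the scoring sentence in SAP 10.2 with a rule that sets the total to 10 times the mean of the answered items when a stated minimum is answered, and to missing otherwise, at Visit 1 and at all later visits alike. Eight of ten is a reasonable minimum, but it is a convention and not a figure from the documents. This has the same form as the NRS rule in SAP 10.1. Add a matching sentence for the domains, for example prorating when at most one item is blank. Then either align protocol 8.6.2 and Appendix B or record the difference in SAP 2.1, which at present declares the SAP consistent with the protocol.

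The cost is two sentences in the SAP, a line or so of derivation code, and the protocol clarification or SAP note. The downside is that prorating assumes the skipped item resembles the answered ones. If nine items sum to 27 and the skipped one is truly 0, the true total is 27 and the prorated total is 30, an error of 3 the other way. Setting every incomplete total to missing also removes the false change, but it discards the answered items and hands the visit to the general missing-data rule.

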10.7 Efficacy Analysis

The efficacy of LT5001 drug product will be assessed via the following:

Part A:

- Change in mean Worst Itching Intensity using NRS.
- Proportion of patients reduced NRS from baseline with respect to weekly mean of the daily 24-hour Worst Itching Intensity NRS score from baseline to the end of Week 4.
- Change from baseline in 5-D Itch Scale score at the end of Week 4.

CONFIDENTIAL

- Change from baseline in total Skindex-10 Scale score at the end of Week 4.

Part B:

- Change in mean Worst Itching Intensity using NRS.
- Proportion of patients reduced NRS from baseline with respect to the weekly mean of the daily 24-hour Worst Itching Intensity NRS score from baseline to the end of Week 8.
- Change from baseline in 5-D Itch Scale score at the end of Week 8.
- Change from baseline in total Skindex-10 score at the end of Week 8.

Mixed-effect model repeated measures analysis of covariance will be applied to compare the treatment groups for efficacy endpoints (i.e. change of NRS, change from baseline in 5-D Itch Scale, change from baseline in total Skindex-10), with baseline itch and prior anti-itch medication use as covariates, and patient as a random effect.

Proportion of patients improved NRS from baseline (2-points, 3-points, or 4-points) was evaluated at each time point compared between treatment group using logistic regression analysis.

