5.3 Observation and analysis times

Reference Start Date and Study Day

Reference start date is defined as the day of randomization and study day relative to the reference start date will appear in every listing where an assessment date or event date appears.

Study day will be calculated from the reference start date and will be used to show start/stop day of the assessments and events relative to the first administration of study treatment.

- If the date of the event is on or after the reference date, then:

$$\text{Study day} = (\text{date of event} - \text{reference date}) + 1.$$
- If the date of the event is prior to the reference date, then:

$$\text{Study day} = (\text{date of event} - \text{reference date}).$$

In case of that event date is partial or missing, the date will appear partial or missing in the listings, and Study Day, and any corresponding durations will be presented based on the imputations specified in Appendix III; Partial Date Conventions.

Definition of baseline values

The baseline value is defined to be the last value which was assessed before the 1st dose of study medication.

Clinical laboratory data on day 1 (Visit 1) will serve as baseline.

Baseline NRS will use the mean NRS score in the 7-days run-in period.

Baseline of 5D itch and Skindex-10 score will be assessed at Visit 1.

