5.5 Covariates and Strata

In Mixed-effect model repeated measures analysis, baseline itch and prior anti-itch medication use will be considered as covariates for efficacy endpoints in Part B.

Strata is not applicable in this study.

6 Subject Accounting and Disposition

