7.2 Disease characteristics

- Alcohol abuse history within 6 months: Yes, No
- Drug abuse history within 6 months: Yes, No
- Duration from the start of hemodialysis (months) : descriptive statistics

Duration from the start of hemodialysis (months) = [date of given informed consent – start date of hemodialysis) + 1] / 30.44
- Duration from the start of pruritus (months) : descriptive statistics

QMS Document Name: Statistical Analysis Plan	Page 14 of 33
QMS No (include version ref): STF-015-GL.02	Document date: 09JUL2019
CONFIDENTIAL	

Duration from the start of pruitus (months) = [date of given informed consent – start date of pruitus) + 1] / 30.44

For each of the above, if partial dates are recorded, the first day of the month will be imputed for missing day and January for missing month.

- Baseline anti-itch medications
- Baseline Worst Itching Intensity NRS
- Baseline 5D-itch scale total score
- Baseline Skindex-10 scale total score

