As a continuous variable, the data value of NRS on the each visit will be derived based on the average value of the values that each subjects had recorded from the previous visit day to next visit day. Change from baseline in NRS will be summarized as descriptive statistics by overall subjects and treatment group for Part A and Part B. For Part B, it will further be analyzed using mixed-effect model repeated measure analysis of covariance to compare the treatment group considering covariates (baseline itch and prior anti-itch medication use). Additionally, treatment group, time, an interaction term for treatment group and time will be included into the model as factors. The model will be used to estimate the NRS at end of treatment. Least square means and their standard errors, along with their 95% confidence interval (CI) of treatment difference will be calculated.

To perform MMRM, SAS programming will be used as follows.

```
proc mixed data= dataset ;
  class treatment time subject prior_med;
  model NRS=treatment time treatment*time baseline_itch prior_med /solution ddfm=kr;
  lsmeans treatment*time/cl pdiff;
  repeated time/type=un subject=subject;
run;
```

By using derived NRS at the timepoint, the subjects reduced NRS from baseline (≥ 2 -points, ≥ 3 -points, ≥ 4 -points) to each time point will be categorized. It will be summarized by frequency and percentage of subjects. For Part A and B, logistic regression analysis will be further performed to compare treatment group differences at each time-point, providing with odds ratio and 95% CI.

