Skindex-10 scale will be assessed at Visit 1, Visit 5, Visit 7 in Part A and Visit 1, Visit 3, Visit 5, Visit 7, Visit 9 (End of study) in Part B. Baseline of Skindex-10 score will be assessed at Visit 1.

Change from baseline in Skindex-10 Scale at week 4 in Part A and Week 8 in Part B (total score and score for each domain) will be summarized by treatment group and visit. In part A and B, mixed-effect model repeated measure analysis of covariance will be performed to compare the treatment group considering covariates (baseline itch and prior anti-itch medication use)

11 Safety

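### The baseline itch covariate is undefined for the 5-D Itch and Skindex-10 models; if it means the NRS baseline, each scale's own Visit 1 score is left out and precision is lost

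*SAP*

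**What the plan says.** One covariate term serves three outcomes. Protocol 10.7 applies a single model statement to the changes in NRS, 5-D Itch and Skindex-10, "with baseline itch and prior anti-itch medication use as covariates, and patient as a random effect". SAP 5.5 repeats it: "baseline itch and prior anti-itch medication use will be considered as covariates for efficacy endpoints in Part B". SAP 10.1 uses the term for the NRS. SAP 10.2 uses it again, separately, for 5-D Itch and for Skindex-10: "considering covariates (baseline itch and prior anti-itch medication use".

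The only code is in SAP 10.1, for the NRS: "model NRS=treatment time treatment*time baseline_itch prior_med /solution ddfm=kr". SAP 10.2 gives none for the other two scales.

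The baselines themselves are defined one scale at a time in SAP 5.3: "Baseline NRS will use the mean NRS score in the 7-days run-in period" and "Baseline of 5D itch and Skindex-10 score will be assessed at Visit 1". SAP 7.2 lists three separate baseline variables, among them "Baseline Skindex-10 scale total score". None of the three is called baseline itch.

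**The concern.** When a change score is modelled without its own baseline, most of the baseline measurement noise stays in the outcome. Adjusting for a different scale's baseline removes only the part that the two scales share. Any chance difference between arms in the Visit 1 5-D or Skindex-10 score then carries into the estimated effect through regression to the mean. Part B is small (30 per arm in the SAP, 45 in the protocol), so such differences are to be expected.

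An undefined covariate also lets two analysts fit different models from the same SAP. These endpoints receive a two-sided 5% test with a P-value, so the choice should be fixed before unblinding.

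**Working it through.** **Which baseline is meant.** Three things point to the NRS.
- Protocol 5.1.2 and SAP 3.1 describe the diary run-in as the means of establishing the baseline itch NRS. That is where the phrase is attached to a named scale.
- The only coded use of `baseline_itch` is in the NRS model. A programmer who reused that code and changed only the outcome would keep the NRS baseline.
- Where the SAP means the 5-D or Skindex-10 baseline (5.3, 7.2), it names the scale.

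No sentence states the equivalence, so this is the best reading and not an established fact.

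**Size of the loss if it is the NRS baseline.** The plan has no figure to reproduce: no formal sample size calculation was done, and no SD or correlation is given for either scale. All inputs below are therefore assumptions, in units of the scale's variance, with equal SDs at baseline and follow-up and a single follow-up time:
- r01, own baseline with own follow-up: 0.4 to 0.7
- rN0, NRS baseline with own baseline: 0.4 to 0.6
- rN1, NRS baseline with own follow-up: 0.2 to 0.35

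Residual variance of the change score:
- NRS baseline only: 2 − 2·r01 − (rN1 − rN0)²
- own and NRS baselines: 1 − (r01² + rN1² − 2·r01·rN1·rN0)/(1 − rN0²)

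Example with r01 = 0.5, rN0 = 0.6, rN1 = 0.2:
- NRS only: 2 − 1 − 0.16 = 0.84
- both: 1 − (0.25 + 0.04 − 0.12)/0.64 = 0.734
- cut: 1 − 0.734/0.84 = 13%

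| r01 | rN0 | rN1 | NRS only | Own + NRS | Cut |
|---|---|---|---|---|---|
| 0.4 | 0.4 | 0.35 | 1.198 | 0.797 | 33% |
| 0.5 | 0.4 | 0.35 | 0.998 | 0.723 | 27% |
| 0.5 | 0.6 | 0.20 | 0.840 | 0.734 | 13% |
| 0.7 | 0.6 | 0.20 | 0.440 | 0.434 | 1% |

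The first and last rows are the extremes of the grid. The middle rows are the extremes at r01 = 0.5. There the variance ratios are 0.998/0.723 = 1.38 and 0.840/0.734 = 1.14, equivalent to about 38% and 14% more patients.

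**Second check, own baseline instead of NRS baseline.** Here the NRS baseline is assumed to relate to follow-up only through the own baseline (rN1 = r·ρ, writing ρ for r01 and r for rN0, both 0.3 to 0.7). The residual variance is 1 − ρ² with the own baseline and 2(1 − ρ) − [r(1 − ρ)]² with the NRS baseline.
- At ρ = r = 0.5: 0.9375/0.75 = 1.25.
- Over the range, the variance is 1.09 to 1.49 times larger with the NRS baseline.
- An effect with 80% power under own-baseline adjustment has 63% to 77% power under NRS adjustment (71% at ρ = r = 0.5). This holds for 30 and for 45 per arm, because the effect is scaled to give 80% in each case.

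**Outcome form.** The NRS code models the score and not its change. If 5-D and Skindex-10 were coded that way with the NRS baseline, the variance ratio in the second check would be 1.05 to 1.87. With the own baseline in the model, score and change give the same treatment difference, since subtracting the baseline only shifts its coefficient by one.

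**The case against.** The strongest reply is that baseline itch is a template term meaning the baseline of whichever scale is being analysed. Protocol 10.7 writes one model for three outcomes. SAP 10.2 states, in each scale's own paragraph, that its baseline is taken at Visit 1, shortly before the covariate is mentioned. SAP 7.2 has a specific label for the NRS baseline, which 10.2 does not use. The code sits in the NRS section and does not say what would be supplied for another outcome. This reading is open, and under it nothing is lost. A reader might infer that the SAP specifies the wrong baseline; the documents do not support that, because they never equate the term with the NRS baseline.

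A reader might also infer that the secondary results would be biased. Under randomisation they would not be: the estimate is unbiased over repeated trials, and the issue is precision and whatever chance imbalance arises.

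The size is also open to challenge. Every correlation is assumed, the range is wide, and the main grid compares NRS alone with both baselines. Simply swapping one baseline for the other is not sure to gain. At r01 = 0.7, rN0 = 0.6, rN1 = 0.2 the own baseline alone leaves 1 − 0.49 = 0.51, against 0.44 with NRS alone. That criticism stands, and it favours adding the own baseline while retaining the NRS baseline.

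Finally, these are secondary endpoints in a trial with no formal power calculation and no multiplicity control. That limits the weight of the point but does not remove the case for a clarification that costs almost nothing.

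**Conclusion.** The covariate is undefined for two secondary endpoints, its best reading is the NRS baseline, and neither document enters the Visit 1 5-D or Skindex-10 score. If the NRS baseline is used, adding the own baseline cuts residual variance by about 1% to 33% (13% to 27% at r01 = 0.5), on assumed correlations, equal SDs and a single follow-up time. If the own-scale baseline was intended, the loss is zero. The NRS primary analysis is unaffected, because `baseline_itch` suits that outcome. This is a free improvement, not an error that threatens the trial's main conclusion.

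**What to change.** In SAP 5.5 and 10.2, replace the shared term with named variables:
- 5-D Itch model: Visit 1 5-D total and prior anti-itch medication use.
- Skindex-10 model: Visit 1 Skindex-10 total and prior anti-itch medication use.
- Domain scores, if modelled: the Visit 1 score of the same domain.
- Baseline NRS: optional extra covariate in both models. State whether it is included; keeping it avoids the corner case above.

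Give the code for both scales with the outcome (score or change) stated, and define baseline itch in SAP 10.1 as the run-in NRS mean. Make the change before unblinding.

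The cost is SAP wording, one variable in the code and at most one degree of freedom. No new data or visits are needed.
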